#### Interim and final analysis

Since the point estimators regarding proportion of measurements with a NRS  $\geq$ 4, used in our sample size calculation for non-inferiority, were based on a small pilot study they may have limited reliability. We therefore established a Data Safety Monitoring Board (DSMB), including a methodologist, statistician and two clinical experts (anaesthesiologist and thoracic surgeon) to assess whether our study generates sufficient power to answer the research question. When 50% of the observations in the TEA group (control) were completed (n=75), the DSMB performed an interim analysis to evaluate the point estimator and variance of the proportion of NRS measurements ≥4 of the control group and advised whether adjustment of our sample size was necessary. The DSMB only had access to all patients who underwent TEA and could warn the research team of potential risk factors and suspension of inclusions. The interim analysis by the DSMB was performed in January 2023. Based on pain scores of 70 complete TEA patients (4 patients had missing data and 1 patient was treated as TEA but randomized for ICNB) in the ITT analysis, no changes in the sample size were required. The final analysis will be performed when all data of 450 patients is collected. No specific stopping rules apply since the OPtriAL has been classified as having negligible risk for study subjects. The SPIRIT flow diagram in Table 1 of the published protocol (1) demonstrates a complete overview of the schedule of assessments.

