#### Protocol violation, adherence and deviation

Protocol violation is defined as non-adherence to the eligibility criteria, randomization process and study procedures, dictating that all patients should participate voluntarily and undergo an anatomical lung resection by VATS and one of the analgesic techniques (TEA, PVB or ICNB).

Protocol adherence defines that control patients should proceed to PVB catheter placement in case TEA catheter placement was unsuccessful; in case PVB too was unsuccessful, then ICNB should be done. Participants receiving TEA or PVB should have a provisional stop of the continuous analgesia at POD 2 and patients receiving TEA should have opioids administered through the epidural continuous mixture. Accidental luxation of the TEA or PVB catheter after surgery will not be seen as nonadherence.

Although the use of ERATS guidelines for enhanced postoperative recovery were advised by the protocol, it is expected that the level of implementation of each aspect of ERATS differs per hospital, for example the strict use of dexamethasone and 5-HT3 receptor antagonists. In addition, the availability of specific local anaesthetics (e.g. bupivacaine or ropivacaine) may vary and induce small between-hospital differences. To ensure equal distribution of small differences in ERATS aspects, we used treatment centre as stratification factor. Incomplete primary or secondary endpoints are considered a protocol deviation and are handled as missing data.

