#### Intention-to-treat and per-protocol populations

Protocol violations such as not meeting the eligibility criteria, withdrawal from the randomization process, not performing an anatomical lung resection by VATS (conversion to thoracotomy, wedge resection or no resection), not utilizing TEA, PVB or ICNB as analgesic technique, or death on the day of the operation (resulting in unobtainable study results), will result in exclusion of the primary analysis. The ITT population will include all remaining randomized patients.

The PP population will include all patients from the ITT population who have adhered to the protocol. Patients will not be included in the PP population when the order of locoregional analgesic techniques in case of unsuccessful performance (TEA, PVB and then ICNB), the provisional stop at POD 2 in case of TEA of PVB, or when the addition of opioids to the epidural mixture were violated.

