#### Analysis

For appointing non-inferiority, both the ITT and PP will be performed and both should attain to the predetermined non-inferiority margin (the one-sided 98.65% CI upper bound of the difference in proportions not exceeding 17.5%). For superiority (p<0.027), the ITT analysis will be considered as the primary analysis and the PP as a supportive analysis. For secondary outcome measures, solely the ITT analysis will be performed.

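### The listed per-protocol criteria never require receipt of the allocated technique, so a patient randomised to ICNB or PVB but given TEA breaches none of them

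*SAP*

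**What the plan says.** Four parts of the SAP bear on this.

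- **Violation** (Protocol violation, adherence and deviation). Patients should "undergo an anatomical lung resection by VATS and one of the analgesic techniques (TEA, PVB or ICNB"). The matching ground for exclusion from the primary analysis, in the populations section, is "not utilizing TEA, PVB or ICNB as analgesic technique". Any one of the three techniques satisfies both.
- **Adherence** (same section as violation). "Protocol adherence defines that control patients should proceed to PVB catheter placement in case TEA catheter placement was unsuccessful", and to ICNB if that fails too. The POD 2 stop and the epidural opioid are then required of patients according to the technique they receive.
- **Per-protocol set** (Intention-to-treat and per-protocol populations). "The PP population will include all patients from the ITT population who have adhered to the protocol". The exclusions follow: "Patients will not be included in the PP population when the order of locoregional analgesic techniques in case of unsuccessful performance" is breached, and likewise "the provisional stop at POD 2 in case of TEA of PVB, or when the addition of opioids to the epidural mixture were violated".
- **Role of the set** (Analysis). "For appointing non-inferiority, both the ITT and PP will be performed and both should attain to the predetermined non-inferiority margin".

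The section on interim and final analysis, describing the January 2023 look at the TEA group, reports that "1 patient was treated as TEA but randomized for ICNB". The SAP is dated October 2023, after that look.

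**The concern.** In a non-inferiority comparison, intervention patients who are treated with the comparator move the observed difference toward zero, and so toward the conclusion the trial hopes to reach. ITT accepts that dilution by design. Requiring the per-protocol analysis to agree is the usual guard against it. The guard works only if the per-protocol set leaves such patients out, and no listed criterion does so here. If they stay in both sets under their randomised arm, asking for both analyses adds no protection against this kind of crossover. The trial is also unblinded, so a membership rule left to judgement would be applied by people who know the allocation.

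**Working it through.** **Step 1. Test the case against each written rule.** Take a patient randomised to ICNB who receives TEA with epidural opioid and the planned stop.

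- One of the three techniques used: met.
- Fallback order after unsuccessful placement: not engaged. The adherence text states it for control patients, and the exclusion applies only where a placement was unsuccessful.
- POD 2 stop: met.
- Opioid in the epidural mixture: met.

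No listed criterion removes this patient. The same holds for a patient randomised to PVB.

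**Step 2. Reproduce the plan's own figures.** Inputs from the SAP: pilot SDs 19.57 (TEA) and 23.33 (locoregional), pilot means 17.57 and 21.21 (difference 3.64), margin 17.5, one-sided error 0.0135 (z = 2.2115), 150 per arm, 12.6% drop-out.

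- Evaluable per arm: 150 × (1 − 0.126) = 131.1, taken as 131.
- SE = √[(19.57² + 23.33²)/131] = √[(382.98 + 544.29)/131] = 2.66.
- Power = Φ[(17.5 − 3.64)/2.66 − 2.2115] = Φ(3.00) = 99.86%, against the stated 99%.
- An error of 0.0135 in each of two comparisons sharing a control (correlation 0.5) gives a family-wise one-sided error of 0.0250.

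The stated figures hold and are not in dispute.

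**Step 3. Error with crossovers left in.** Assume the true difference among patients who receive the block is exactly 17.5, and that k of 131 intervention patients have the TEA mean and SD. With f = k/131:

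- observed difference d = 17.5 × (1 − f);
- intervention variance v = (1 − f) × 23.33² + f × 19.57² + f(1 − f) × 17.5²;
- SE = √[(19.57² + v)/131];
- chance of declaring non-inferiority = Φ[(17.5 − d)/SE − 2.2115].

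| k | f | d | SE | Φ argument | error |
|---|---|---|---|---|---|
| 0 | 0 | 17.50 | 2.66 | −2.21 | 0.0135 |
| 1 | 0.8% | 17.37 | 2.66 | −2.16 | 0.0153 |
| 2 | 1.5% | 17.23 | 2.66 | −2.11 | 0.0174 |
| 5 | 3.8% | 16.83 | 2.67 | −1.96 | 0.0249 |
| 13 | 9.9% | 15.76 | 2.68 | −1.56 | 0.0591 |

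**Step 4. Place the documented case.** The interim group was 75 patients (70 complete, 4 with missing data, 1 crossover). If the arms accrued equally, about 75 had been randomised to ICNB, so the rate is about 1/75 = 1.3%. Carried to 131 patients, that is between 1 and 2 crossovers, an error of about 0.015 to 0.017. Rows above k = 2 are assumptions.

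**Step 5. Cost of removing them.** At the pilot difference, with n intervention patients left, power = Φ[13.86/√(382.98/131 + 544.29/n) − 2.2115].

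- n = 130 (1 removed): SE 2.67, power 99.9%.
- n = 118 (13 removed): SE 2.75, power 99.8%.

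**The case against.** **The general clause may already cover it.** The per-protocol set is for patients who adhered to the protocol, and nothing says the list of exclusions is closed. On an ordinary reading, a patient given another arm's technique without a permitted reason did not adhere, and the protocol itself is not shown. This stands in part: the text is ambiguous, and it cannot be said that the SAP definitely keeps such patients. But the SAP spells out adherence, and the exclusions repeat the same three items without this one.

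**The violation rule mentions the randomisation process.** The populations section renders this as withdrawal from that process. Stretching it to crossover would remove the patient from ITT as well, which is worse. It also sits badly with the interim section, which sets the ICNB patient apart from the TEA patients under ITT.

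**The set may be analysed as treated.** The SAP does not state the grouping. Its treatment of the interim patient fits grouping as randomised, but that is an inference.

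**A reader might infer that the reported patient is certain to be counted as ICNB in the per-protocol analysis.** The SAP does not support that. It gives no reason for the switch and does not say whether the epidural contained opioid or was stopped as planned. If the switch followed an unsuccessful ICNB, the order rule might apply.

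**A reader might also infer that 12.5% crossover would turn a true 20-point deficit into a pass, since 20 × 0.875 = 17.5.** That compares the point estimate with the margin, whereas the decision uses the upper limit of the one-sided 98.65% interval. At 12.5% crossover that limit is expected near 17.5 + 2.21 × 2.69 = 23.5, and the chance of a pass is 1.35%.

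**Exclusions will be visible.** The Trial population section promises numbers excluded from each set with reasons. That shows afterwards what was done, but does not fix the rule beforehand.

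**Conclusion.** The point holds as a gap in the definition of a population on which the non-inferiority decision rests. It is not a demonstrated bias. Allocation to a different technique is not a listed ground for leaving the per-protocol set, although the SAP itself reports such a mismatch from before it was written.

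The one documented case would move the error only from 0.0135 to about 0.015. It would take around 5 crossovers in an arm to reach 0.025 and 13 to reach 0.059, and nothing in the SAP shows such numbers. The interim look covered the TEA-treated patients, where switches into TEA would appear, and reports one from ICNB and none from PVB.

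The calculation assumes a normal approximation, pilot SDs, 131 per arm in the per-protocol set, analysis by randomised arm, a true difference exactly at the margin, and crossovers who respond like the TEA arm. The return to 0.0135 after removal assumes that removal causes no selection.

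**What to change.** In the section on intention-to-treat and per-protocol populations:

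1. Add a fourth per-protocol exclusion: the patient received a technique other than the one allocated, unless through the SAP's prescribed fallback after unsuccessful placement.
2. State that these patients remain in the ITT set in their randomised arm.
3. State that the per-protocol set is analysed by randomised arm.
4. Report the number of such patients by arm in the flow diagram (Figure 1).

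This takes a few sentences. The rule needs only the allocated and the received technique, and Table 2 already plans to report how each technique was carried out. A few patients leave the per-protocol set, with negligible loss of power (99.8% under the pilot assumptions even with 13 removed from one arm). Control patients who reach PVB or ICNB by the prescribed fallback would stay in the per-protocol control arm, as the SAP now has it. They also draw the arms together, so their number should be shown beside the crossovers.

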#### **Trial population**

All screened patients assessed for eligibility and receiving the patient information folder will be recorded. The number of patients not randomized or excluded from the ITT and PP analysis will be

reported with reasons (e.g. withdrawal or lost to follow-up). Similarly, the number of randomized patients per analgesic group as well as the number of patients in the ITT and PP analysis will be reported. Progress of all participants through the trial is depicted in Figure 1.

#### Baseline characteristics

Baseline characteristics will be described by trial arm as illustrated in Table 1 and assessed descriptively for the ITT group. In case of missing data, the denominator will not match with the total number of patients and this will be indicated in the corresponding table. Missing baseline characteristics will not be imputed.

Since stratification and randomization are applied to ensure a balanced distribution of baseline characteristics, we assume any differences to be caused by chance and to be a property of the sample, not of the population. Nevertheless, an imbalance of prognostic factors should not be ignored as it can influence the estimation of treatment effects. Therefore, all baseline characteristics in Table 1 will be compared between TEA versus PVB and TEA versus ICNB by using a validated method of standardized mean differences (SMDs) as described by Nguyen et al (9). The SMDs for these important prognostic variables will be reported in Table S1 (Supplemental material) and identified as potential imbalanced factors when the SMD exceeds 25%.

In Table 2, we will portray all details regarding the execution of the analgesic techniques including when it was performed (before, at the beginning, at the end or after the operation) and medication given (type, dosage and volume). For the TEA group we will report the test dose and continuous epidural mixture (local anaesthetics and opioids). The infusion rate (numerical in mL) from the time of placement until removal of the epidural catheter will be noted to calculate a total dosage (in milligram [mg] or microgram [ug]) of mixture given, reported as a continuous outcome. For the PVB group, the initial perioperative bolus given and the continuous infusion rate (in mL) until the day the PVB is stopped, will be recorded. For both TEA and PVB, also the number of days continuous infusion

was given will be noted. For the ICNB group the local anaesthetic given and the number of covered intercostal levels will be recorded. Any complication occurring during the execution of the analgesic technique will be reported in the text of the manuscript. Surgical and (general) anesthesia baseline characteristics will be shown in detail in Table 1.

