#### Pain scores during rest and mobilisation

Pain scores in rest and during mobilisation will be registered at: baseline (pre-operatively); at the recovery room and in the evening of POD 0; in the morning, afternoon, and evening of POD 1-3 and at the follow-up appointment, generating 13 moments in which the pain scores are prospectively measured. Since pain scores are repeated measurements from the same patient, they are likely to be correlated and we cannot assume independency. As we expect the effect of analgesia is patient-specific and will therefore vary substantially from patient to patient, a linear mixed model will be used (Figure 3a). This analysis will lead to a more precise estimate of the trend in pain scores and how this outcome changes over time per analgesic technique. The model will include random intercepts, and baseline scores, time of the measurement and treatment group as fixed effects. The

linear mixed model will accommodate unbalanced data patterns by assuming missing data at random and use all available observations and patients in the analysis (10). We will apply the covariance matrix that fits best according to Akaike's Information Criterion (AIC) (11).

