#### Patient replacement and missing data

In the sample size calculation, we have considered 12.6% extra inclusions due to drop-outs after conversions to thoracotomy (late exclusion). Since this percentage is appropriately represented by data from the Dutch Clinical Audit database from 2017, we do not expect further patient

replacement. Clinical data management is performed by independent professional data managers from the Dutch Comprehensive Cancer Centre. Once inclusions are complete, careful inspection of the data will take place. The mechanism causing data to be missing, whether it is (completely) at random or not at random, will guide the study group to apply analytical methods to amend missing data.

The incidence of missing data is partially limited by study design where minimum numbers of measurements suffice to generate an outcome value. For our non-inferiority research question regarding pain, complete cases include patients with at least 3 NRS measurements during POD 0 until 2 or a LOS  $\leq$  2 days, to allow detection of curvilinear pain patterns over time for reliable imputation. The cut-off for LOS  $\leq$  2 days is established due to the expectation that patients who have been discharged from the hospital have a NRS score  $\leq$  4 (standard of care). For our superiority question regarding QoR, complete cases include patients with at least one QoR-score during POD 0 until 2.

In case of remaining patients with lacking outcome data below 5% of the study size (14), the baseline Table 1 will be reproduced for patients intended to be included in the analysis as complete cases and added to the supplementary material (15). Imbalances in covariate distributions across groups derived from observed SMDs in this table, will be assessed from a clinical perspective for potential bias in prognosis and adjusted for in a primary analysis based on complete cases.

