#### Additional analyses

Multiple regression of both co-primary outcomes will be done to explore and adjust for the impact of potential baseline imbalances (SMDs exceeding 25%). If opportune, adjusted contrasts between analgesic techniques will be reported.

Also, exploratory analyses will be done on primary and secondary outcomes per treatment centre (strata).

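### The no-imputation rule for baseline data is the SAP's only rule for a missing covariate, so the adjusted co-primary models and the pain mixed model can lose patients who have outcome data

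*SAP*

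**What the plan says.** Under Baseline characteristics, the SAP describes Table 1, accepts that denominators may fall short of the group size, and ends: "Missing baseline characteristics will not be imputed". It makes no exception for values used in a model.

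Baseline values are used in models in three places:

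- Additional analyses: "Multiple regression of both co-primary outcomes will be done to explore and adjust for the impact of potential baseline imbalances", where an imbalance is a standardised mean difference (SMD) above 25%.
- Patient replacement and missing data: imbalances judged from a clinical perspective are to be "adjusted for in a primary analysis based on complete cases".
- Pain scores during rest and mobilisation: "The model will include random intercepts, and baseline scores, time of the measurement and treatment group as fixed effects". The same paragraph says the model will assume data missing at random and "use all available observations and patients in the analysis".

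Complete cases are defined without reference to covariates. For pain, "complete cases include patients with at least 3 NRS measurements during POD 0 until 2 or a LOS" of at most 2 days; for QoR, "complete cases include patients with at least one QoR-score during POD 0 until 2". Multiple imputation is considered only when missing outcome data reach 5% of the study size and are judged missing completely at random, and then only to support the primary analysis.

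**The concern.** A regression or mixed model cannot use a row whose fixed-effect covariate is missing. The missing-at-random likelihood of a mixed model deals with missing responses, not missing covariates. If the pre-operative pain score is a covariate and is absent, the patient's post-operative scores all leave the model. In the co-primary regressions, a patient who meets the SAP's own definition of a complete case can still drop out for want of one Table 1 value.

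Two things are at stake. Precision falls in the adjusted and secondary models. And the adjusted and unadjusted estimates then rest on different patients, so the difference between them no longer shows the effect of adjustment alone.

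**Working it through.** **Inputs from the SAP.** 150 patients per arm; 12.6% drop-out; non-inferiority power 99% at one-sided 0.0135; QoR power 90% at two-sided 0.027; margin 17.5 points; pilot proportions 17.57 (SD 19.57) and 21.21 (SD 23.33).

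**Input assumed.** The SAP gives no rate of missing baseline data. I take 3% and 5% per covariate, missing independently, with one or three covariates.

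**The plan's own power first.** Evaluable per arm: 150 × (1 − 0.126) = 131, or 393 in all. Pooled SD = √((19.57² + 23.33²)/2) = 21.53. The pilot difference is 21.21 − 17.57 = 3.64. Non-inferiority power = Φ((17.5 − 3.64)/(21.53 × √(2/131)) − 2.2115) = 99.86%, consistent with the stated 99%. The QoR difference and SD are not in the SAP, so I use the effect implied by 90% power at 131 per arm: (2.2115 + 1.2816) × √(2/131) = 0.432 SD.

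**How likely is an adjusted model?** With 131 per arm and no true difference, the chance that one continuous-like variable exceeds an SMD of 0.25 is 2 × (1 − Φ(0.25/√(2/131))) = 4.3%. Table 1 has about 33 variables, so 33 × 0.043 = 1.4 flags are expected per comparison. The chance of at least one is 1 − (1 − 0.043)^33 = 77% if they were independent, which they are not exactly. Adjustment is a realistic prospect, usually for few covariates.

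**Size of the loss.** With k covariates each missing in a share m, the share kept is (1 − m)^k. QoR power = Φ(0.432 × √(n/2) − 2.2115), ignoring precision gained from the covariates.

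| Covariates | Missing each | Share kept | n per arm | Lost of 393 | QoR power |
|---|---|---|---|---|---|
| 0 | – | 1.000 | 131 | 0 | 90% |
| 1 | 3% | 0.970 | 127 | 12 | 89.0% |
| 1 | 5% | 0.950 | 124 | 20 | 88.4% |
| 3 | 3% | 0.913 | 120 | 34 | 87.0% |
| 3 | 5% | 0.857 | 112 | 56 | 84.7% |

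Non-inferiority power barely moves: with five covariates at 5% missing, about 101 per arm remain and power is 99.1%.

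**The mixed model, text against text.** The paragraph counts 13 measurement moments: 1 at baseline, 2 on day 0, 9 on days 1 to 3 and 1 at follow-up. That count, Appendix A and Figure 3a treat baseline as a time point of the outcome. The sentence that specifies the model treats it as a fixed effect. Under the first reading, a patient without a baseline score keeps the other 12 moments and the claim of full use holds. Under the second, the patient is lost and the claim fails. The SAP does not choose.

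**The case against.** The strongest reply is that the quoted sentence concerns a descriptive table and was never meant to govern models. It closes the Table 1 paragraph, and the pre-operative pain score is not a row of Table 1 or Table S1, so it reaches the mixed model only by extension. The SAP never states listwise deletion; that is inferred from how such models are ordinarily fitted. All of this stands. It does not close the gap, because no other sentence says what happens to a missing covariate.

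A reader might infer that the trial's main tests lose patients or power. The documents do not support that. The pain decision uses an unadjusted confidence bound, and Appendix A gives QoR an unpaired t-test or Mann-Whitney test; neither needs a covariate. The regression under Additional analyses is exploratory and reported if opportune. The point touches a primary analysis only where the missing-data section's own adjustment is carried out.

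A reader might also infer bias. None is shown: if a covariate is missing for reasons unrelated to outcome, the complete-case estimate remains unbiased and only precision and comparability suffer.

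Finally, a reader might conclude that simple filling is safe for all of Table 1, since baseline values are independent of the arm. That fails here. Table 1 includes operating time, intra-operative drugs and pathological stage. Table 2A allows for pre-operative epidural placement, so allocation comes before these items, and randomisation does not guarantee that they are independent of it.

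**Conclusion.** The point holds for the adjusted co-primary models and, if the baseline score is a covariate, for the pain mixed model. There the SAP's text, fitted in the ordinary way, omits patients with usable outcomes, and in the mixed model that conflicts with its stated coverage. It is not a flat contradiction, because modelling baseline as a response would remove the conflict.

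The effect is modest under the assumed rates: about 1 to 2 percentage points of QoR power with one covariate, and about 3 to 5 with three. These figures depend on assumed, independent missingness and on the implied effect of 0.432 SD. They overstate the loss to the extent that prognostic covariates add precision. The true size is unknown. It is worth correcting because the change is nearly free and is best settled before the data are analysed.

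**What to change.** 1. Limit the no-imputation sentence to the descriptive tables (Table 1 and Table S1).
2. Add a rule for adjusted and mixed models: a missing covariate measured before randomisation, including pre-operative NRS and QoR-15 where used as covariates, is filled by the overall mean if continuous or a separate missing category if categorical. Both are computed without regard to arm, so every patient with outcome data stays in. Randomisation makes such values independent of the arm, so the filling does not bias the treatment comparison.
3. State whether the pre-operative score in the mixed model is a covariate, in which case rule 2 applies, or a response. Modelling it as a response is an acceptable alternative that needs no filling.
4. Say explicitly that rule 2 and its justification do not cover Table 1 items arising after randomisation, such as operating time, intra-operative drugs and pathological stage. Whether to adjust for these at all needs a separate decision.

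The cost is a few sentences in the SAP and a few lines of analysis syntax. No new data are needed, and the sample size and unadjusted co-primary tests do not change.
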